## 7. EXPECTED TOXICITIES AND DOSING DELAYS/DOSE MODIFICATIONS

### 7.1 Dose Modification Based on Adverse Events

- 7.1.1 Dose modifications based on Adverse Event documented prior to each cycle of treatment. Strictly follow the modification in the table provided below until individual treatment tolerance can be ascertained. If multiple adverse events occur, administer the dose based on the greatest dose reduction required for any single adverse event observed. Dose modifications apply to the treatment given in the preceding cycle and are based on adverse events observed in the prior dose.
- 7.1.2 Note that fulvestrant administration is not modified for any adverse event.
- If alisertib is held due to toxicity then fulvestrant should also be held. Both agents should be restarted together.
  - If alisertib is discontinued due to intolerability then fulvestrant is also discontinued.
- 7.1.3 If treatment is held greater than 21 days without resolution of any adverse events other than severe neutropenia or a 3rd dose reduction is required then study treatment is to be discontinued\* and the patient will enter the Event Monitoring phase of the study.(see Section 14.0).  
\*Note: If patient is deriving benefit from study treatment and the event can be managed safely, consult Study Chair ([name]) regarding continuation.
- 7.1.4 Dose reduction levels

Dose Level	Alisertib (twice daily) Days 1-3, 8-10, 15-17
-1	40 mg
-2	30 mg

→ → Use the NCI Common Terminology Criteria for Adverse Events (CTCAE) version 4.0\* unless otherwise specified ← ←

\* Located at [REDACTED]

### 7.2 Dose Modifications – Prior to each cycle of treatment

Strictly follow the modification in the table provided below until individual treatment tolerance can be ascertained. If multiple adverse events occur, administer the dose based on the greatest dose reduction required for any single adverse event observed. Dose modifications apply to the treatment given in the preceding cycle and are based on adverse events observed in the prior dose.

CTCAE System/ Organ/ Class (SOC)	ADVERSE EVENT	ACTION**
Blood and lymphatic system disorders	Anemia Grade 3 with hemoglobin <7.0 g/dL or Grade 4	
First or Second Episode: Hold alisertib administration until recovery to ≤Grade 2 or baseline then decrease by 1 dose level
 
If not recovered within 14 days discontinue alisertib and proceed to event monitoring phase*
 
Third Episode: Discontinue study treatment (see note*).
 
*NOTE: If patient is deriving benefit from study treatment and event can be managed safely, consult Study Chair regarding continuation.

Investigations	Neutrophil Count Decreased Grade 3 (neutrophils <1000 - 500 cells/mm  )	
First Episode: Hold alisertib administration and check neutrophil counts within 5-7 days of report of Grade 3 ANC (referred to as ANC recheck #1).
 
(a) results of ANC recheck #1
 
 
- If neutrophils ≥1500 cells/mm^3, resume alisertib at current dose
 
- If neutrophils <1500 cells/mm^3, continue to hold alisertib and re-check neutrophils counts again within the next 7 days but at most 14 days after the first report of Grade 3 ANC (ANC recheck #2)
 
 
(b) results of ANC recheck #2
 
 
▪ If neutrophils ≥1500 cells/mm^3, resume alisertib at one dose lower
 
▪ If neutrophils remain <1500 cells/mm^3 14 days after first report of Grade 3 ANC, discontinue study treatment* 

 
Second Episode: Hold alisertib administration and check neutrophil count within 5-7 days of report of Grade 3 ANC (referred to as ANC recheck #1).
 
(a) results of ANC recheck #1
 
 
- If neutrophils ≥1500 cells/mm^3, resume alisertib at first dose level below current dose level
 
- If neutrophils <1500 cells/mm^3, continue to hold alisertib and re-check neutrophils counts again within the next 7 days but at most 14 days after the first report of Grade 3 ANC (ANC recheck #2)
 
 
(b) results of ANC recheck #2
 
 
▪ If neutrophils ≥1500 cells/mm^3, resume alisertib at first dose level below current dose
 
▪ If neutrophils remain <1500 cells/mm^3 14 days after first report of Grade 3 ANC in this second episode, discontinue study treatment* 

 
Third Episode: discontinue study treatment (see note*)
 
*NOTE: If patient is deriving benefit from study treatment and event can be managed safely, consult Study Chair regarding continuation.

Investigations	Neutrophil count decreased Grade 4 (neutrophils <500 cells/mm  )	
First Episode: Hold alisertib administration and check neutrophil counts within 5-7 days of report of Grade 4 ANC (referred to as ANC recheck #1).
 
(a) results of ANC recheck #1
 
 
▪ If neutrophils <math>\geq 1500</math> cells/mm^3, resume alisertib at first dose level below at current dose
 
▪ If neutrophils <1500 cells/mm^3, continue to hold alisertib and re-check neutrophils counts again within the next 7 days but at most 14 days after the first report of Grade 4 ANC (ANC recheck #2)
 
 
(b) results of ANC recheck #2
 
 
▪ If neutrophils <math>\geq 1500</math> cells/mm^3, resume alisertib at first dose level below at current dose
 
▪ If neutrophils remain <1500 cells/mm^3 14 days after first report of Grade 4 ANC, discontinue study treatment* 

 
Second Episode: Hold alisertib administration and check neutrophil counts within 5-7 days of report of Grade 4 ANC results of ANC recheck #1
 
(a) results of ANC recheck #1
 
 
▪ If neutrophils <math>\geq 1500</math> cells/mm^3, resume alisertib at first dose level below current dose
 
▪ If neutrophils <1500 cells/mm^3, continue to hold alisertib and re-check neutrophils counts again within the next 7 days but at most 14 days after the first report of Grade 4 ANC (ANC recheck #2)
 
 
(b) results of ANC recheck #2
 
 
▪ If neutrophils <math>\geq 1500</math> cells/mm^3, resume alisertib at first dose level below at current dose
 
▪ If neutrophils remain <1500 cells/mm^3 14 days after first report of Grade 4 ANC, discontinue study treatment* 

 
Third Event: Discontinue study treatment (see note*)
 
*NOTE: If patient is deriving benefit from study treatment and event can be managed safely, consult Study Chair regarding continuation.

Investigations	Platelet count decreased Grade 1 and 2 (<100,000 cells/mm  but >50,000 cells/mm  )	
Hold alisertib administration and check platelet counts every 3-5 days until platelets <math>\geq 100,000</math> cells/mm^3 or for a maximum of 21 days after Grade 1-2 decrease in PLT reported
 
If platelet count recovered to <math>\geq 100,000</math> cells/mm^3 within 21 days then resume alisertib at current dose
 
Otherwise discontinue study treatment *
 
*NOTE: If patient is deriving benefit from study treatment and event can be managed safely, consult Study Chair regarding continuation

Investigations	Platelet count decreased Grade 3 (25,000 – 50,000 cells/mm  )	
First Episode: Hold alisertib administration and check neutrophil counts within 5-7 days of report of Grade 3 PLT (referred to as PLT recheck #1)
 
(a) results of PLT recheck #1
 
 
▪ If platelets <math>\geq 100,000</math> cells/mm^3, resume alisertib at current dose
 
▪ If platelets <math>< 100,000</math> cells/mm^3, continue to hold alisertib and re-check platelet count again within the next 5- 7 days but at most 14 days after the first report of Grade 3 ANC (ANC recheck #2)
 
 
(b) results of PLT recheck #2
 
 
▪ If platelets <math>\geq 100,000</math> cells/mm^3, resume alisertib at first dose level below at current dose
 
▪ If platelets remains <math>< 100,000</math> cells/mm^3 14 days after first report of Grade 3 PLT decrease, discontinue study treatment
 
 
Second Episode: Hold alisertib administration and check platelet counts within 5-7 days of report of Grade 1 ANC results of ANC recheck #1
 
(a) results of PLT recheck #1
 
 
▪ If platelets <math>\geq 100,000</math> cells/mm^3, resume alisertib at current dose
 
▪ If platelets <math>< 100,000</math> cells/mm^3, continue to hold alisertib and re-check platelet counts again within the next 7 days but at most 14 days after the first report of Grade 3 PLT (PLT recheck #2)
 
 
(b) results of PLT recheck #2
 
 
▪ If platelets <math>\geq 100,000</math> cells/mm^3, resume alisertib at first dose level below at current dose
 
▪ If platelets remains <math>< 100,000</math> cells/mm^3 14 days after first report of Grade 3 PLT decrease, discontinued 14 days after first report of Grade 3 ANC, discontinue study treatment
 
 
Third Event: Discontinue all study treatment (see note*)
 
*NOTE: If patient is deriving benefit from study treatment and event can be managed safely, consult Study Chair regarding continuation.

	Platelet count decreased Grade 4 ( $< 25,000$ /mm  ) or Grade 3 with bleeding	
Discontinue all study treatment*
 
*NOTE: If patient is deriving benefit from study treatment and event can be managed safely, consult Study Chair regarding continuation.

Blood and lymphatic system disorders	
Febrile neutropenia
 
Grade 3 (neutrophils <1000 cells/mm^3 with a single temperature of >38.3°C (101°F) or a sustained temperature of ≥38°C (100.4°F) for more than one hour)
 
Grade 4 (Life threatening consequences)
	
Discontinue all study treatment*
 
*NOTE: If patient is deriving benefit from study treatment and event can be managed safely, consult Study Chair regarding continuation.

Gastrointestinal disorders	Mucositis oral Grade 3 or 4	
First event: Hold alisertib administration until recovered to ≤Grade 1 or pre-treatment level If recovered Grade 1 or baseline within 21 days, continue alisertib one dose level below current dose level
 
Second event: Hold alisertib administration until recovered to ≤Grade 1 or pre-treatment level If recovered to ≤Grade 1 or baseline within 21 days, continue alisertib one dose level below current dose level If not, discontinue all study treatment*
 
Third event: Discontinue all study treatment (see note*)
 
*NOTE: If patient is deriving benefit from study treatment and event can be managed safely, consult Study Chair regarding continuation.

Nervous system disorders	Somnolence ≥Grade 3	
Hold alisertib administration until recovered to ≤Grade 1 or pre-treatment level If recovered to ≤Grade 1 or baseline within 14 days, continue alisertib one dose level below current dose level If not, discontinue all study treatment (see note*)
 
NOTE: Evaluate whether patient alcohol consumption or utilization of benzodiazepines are contributing. If so, counsel patient to restrict alcohol and discontinue benzodiazepines with provider guidance.
 
*NOTE: If patient is deriving benefit from study treatment and event can be managed safely, consult Study Chair regarding continuation

Other unspecified adverse event reduction instructions	≥Grade 3	
Hold alisertib administration until recovered to ≤Grade 1 or pre-treatment level (baseline level) If recovered to ≤Grade 1 or baseline within 14 days, continue alisertib one dose level below current dose level If not, discontinue all study treatment *
 
*NOTE: If patient is deriving benefit from study treatment and event can be managed safely, consult Study Chair regarding continuation

### 7.3 Dose Modifications – Cycle 1 Day 15

The following dose modifications apply to adverse events documented on Cycle 1 Day 15 and the first crossover Cycle 1 Day 15.

Investigations	Neutrophil count decreased Grade 3 or 4 (neutrophils <1000 cells/mm  )	Omit Cycle 1 Days 15-17 administration of alisertib Administer fulvestrant loading dose Check neutrophil count on Cycle 2 Day 1
----------------	--	---

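### The Grade 3 platelet row of the dose-modification table carries over neutrophil wording in four lines; the intent can be inferred, but the text is wrong as written

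*Combined protocol and SAP*

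**What the plan says.** Section 7.2 is introduced with the instruction "Strictly follow the modification in the table provided below until individual treatment tolerance can be ascertained". The row for a Grade 3 platelet decrease (25,000 to 50,000 cells/mm³) sets out a first and a second episode. Each has a hold, a first recheck, a second recheck and a stop rule. Four lines of the row refer to neutrophils:

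- First episode, recheck #1: "Hold alisertib administration and check neutrophil counts within 5-7 days of report of Grade 3 PLT". The same sentence labels this check PLT recheck #1.
- First episode, recheck #2: "re-check platelet count again within the next 5- 7 days but at most 14 days after the first report of Grade 3 ANC", labelled ANC recheck #2.
- Second episode, recheck #1: "check platelet counts within 5-7 days of report of Grade 1 ANC results of ANC recheck #1".
- Second episode, stop line: "14 days after first report of Grade 3 PLT decrease, discontinued 14 days after first report of Grade 3 ANC, discontinue study treatment".

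The neighbouring row for Grade 1 and 2 platelet decreases refers to platelets only: "Hold alisertib administration and check platelet counts every 3-5 days until platelets".

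**The concern.** This is operative dosing text, not background. Read literally, it orders a neutrophil count to follow up thrombocytopenia. It counts one recheck from a Grade 3 neutrophil report and another from a Grade 1 neutrophil report. It also gives the second-episode discontinuation rule two starting points. Section 7.2 manages neutrophil decreases only at Grades 3 and 4, so a Grade 1 neutrophil report is not an event that the table handles at all.

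What is at stake is whether sites apply the platelet hold and stop rules in the same way. Section 8.1.7 lists both neutropenia and thrombocytopenia among the very common toxicities of alisertib (above 10%, with no grade given), so the two can plausibly occur together.

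**Working it through.** No figure in the plan is to be reproduced. The check is to read the row line by line, compare it with the neutrophil rows, and work out what the wrong dates would change.

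**1. The six time limits in the row**

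| Step | Test named | Event the clock runs from |
|---|---|---|
| First episode, recheck #1 | neutrophils (wrong) | Grade 3 PLT |
| First episode, recheck #2 | platelets | Grade 3 ANC (wrong) |
| First episode, stop | platelets | Grade 3 PLT |
| Second episode, recheck #1 | platelets | Grade 1 ANC (wrong count and grade) |
| Second episode, recheck #2 | platelets | Grade 3 PLT |
| Second episode, stop | platelets | Grade 3 PLT and Grade 3 ANC (doubled) |

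Three of six limits name ANC: two name ANC alone and one names both. If the doubled stop sentence is split, there are seven dates, 3 ANC and 4 PLT. Neutrophils are named once and ANC five times, so 1 + 5 = 6 wrong phrases in four lines.

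**2. Where the wording comes from**

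The Grade 3 neutrophil row contains "but at most 14 days after the first report of Grade 3 ANC (ANC recheck #2", the same phrase that appears in the platelet row. The Grade 4 neutrophil row has, at its second episode, "check neutrophil counts within 5-7 days of report of Grade 4 ANC results of ANC recheck #1"; the platelet row's second-episode line ends in the same way. The wrong words sit inside complete phrases with a visible source. That points to copying from the neutrophil rows, not to damage in reading the PDF.

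**3. What the rest of the row shows**

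Each episode has four decision thresholds, so 4 × 2 = 8, and all eight are platelet counts. Six recheck labels say PLT and two say ANC. A neutrophil result cannot settle any branch of the row.

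**4. First-episode recheck #2**

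Counted from the platelet report, this check falls between day 5 + 5 = 10 and day 7 + 7 = 14, provided that recheck #1 is on time. A 14-day cap from the platelet report is therefore already met. A cap counted from a later neutrophil report would not bind either, and one counted from an earlier report could only bring the check forward.

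**5. Second-episode stop line**

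Let the Grade 3 platelet report that starts the hold be day 0, and let Grade 3 neutropenia be reported d days later.

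- Platelet date: day 14.
- Neutrophil date: day 14 + d.
- Difference: d days.
- Sections 7.1.3 and 6.4.4 end treatment once a hold or delay exceeds 21 days, so the extra hold is at most 21 − 14 = 7 days, that is, min(d, 7).

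For illustration, d = 3 gives 3 extra days and d = 10 gives 7. If d = 0 the dates agree. If the neutrophil report came first, the second date would fall before day 14 and the hold would not be lengthened. Without Grade 3 neutropenia there is only the platelet date.

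**The case against.** The strongest reply is that this is a proofreading slip that no competent site would misapply. The row heading fixes the event. The misworded first check is itself labelled a platelet recheck, and both branches beneath it need a platelet value. Platelets and neutrophils belong to the same hematology group in Sections 11.1 and 11.2, so either order would yield both results. Nearly all of this stands, and it sets the severity.

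A reader might infer that the second-episode first recheck has no usable start date. The documents do not support that. The line tells the site to hold drug and check platelets. The parallel first-episode line counts 5 to 7 days from the Grade 3 platelet report, and the next second-episode step is capped at 14 days from that same report. The named date is wrong, but the right one can be recovered from the row.

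A reader might also infer that the doubled stop line leaves the hold open-ended. It does not. The platelet date comes first in the sentence and is a complete criterion. Concurrent Grade 3 neutropenia has its own 14-day stop rule in its own row. Section 6.4.4 makes a delay of more than 21 days a reason to stop all protocol therapy; its only exception is for Cycle 1 Day 15 severe neutropenia. Section 7.1.3 sets the same limit for unresolved events other than severe neutropenia, and Section 6 requires contact with the Study Chair for any interruption of 21 days or more.

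Finally, the instruction to follow the table strictly applies only until a patient's tolerance is known, and two of the four faulty lines concern a second episode. That softens the instruction but does not make the wording right.

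**Conclusion.** Minor, and wrong as written. The Grade 3 platelet row orders the wrong test once, names the wrong starting event twice, and gives its second-episode stop rule two starting events. No other section corrects it. The intended test and dates can be inferred from the row itself.

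The one real ambiguity is the stop line. It requires a second Grade 3 platelet episode, platelets still below 100,000 cells/mm³ at 14 days, and Grade 3 neutropenia reported on a different day. Its cost is an extra hold of no more than about 7 days, unless the Study Chair agrees to continuation. That bound assumes the hold starts at the Grade 3 platelet report.

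The documents give no rate for Grade 3 thrombocytopenia or for its occurrence together with neutropenia, so the frequency is unknown. The error does not touch the primary endpoint, the sample size, the analysis or the safety stopping rule.

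**What to change.** Reword four lines of the row:

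- First episode, recheck #1: name platelet counts as the test; keep 5 to 7 days from the Grade 3 PLT report and the label PLT recheck #1.
- First episode, recheck #2: count the 14-day cap from the first Grade 3 PLT report and label the check PLT recheck #2.
- Second episode, recheck #1: count the 5 to 7 days from the Grade 3 PLT report and label the check PLT recheck #1.
- Second episode, stop line: keep one criterion only, which is to stop if platelets are still <100,000 cells/mm³ 14 days after the first Grade 3 PLT report of this second episode. The Grade 3 neutrophil row already ties its own stop line to the second episode in this way.

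These edits remove all six wrong phrases. They alter no threshold, interval or dose and add no blood test. Section 15.1 requires approval of any amendment by each institution's IRB, so the correction should be bundled with the next amendment and not issued alone.

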## 8. DRUG FORMULATION/STORAGE/SUPPLY

### 8.1 Alisertib (MLN8237, ML00653668)

Alisertib is an investigational agent and will be supplied free-of-charge from Millennium.

8.1.1 **Background:** Alisertib is a selective small molecule inhibitor of Aurora A kinase inhibitor that is being developed for the treatment of advanced malignancies. Aurora A is expressed and active during mitosis. Alisertib is also expected to be toxic to proliferating normal tissues, such as the bone marrow, GI epithelium, and hair follicles, since any cell that is in mitosis, where Aurora A is expressed and active, should be susceptible to the effects of an Aurora A kinase inhibitor. The Aurora A kinase gene is amplified, overexpressed, or both, in many tumors including: colon, breast, pancreatic, and bladder cancers, as well as certain lymphomas, leukemias, and myeloma.

8.1.2 **Formulation:** Alisertib is supplied as enteric-coated tablets, formulated with the sodium salt of MLN8237 (MLN8237-004).

The enteric-coated tablet (ECT) dosage form of alisertib is available as 10 and 15 mg strengths, expressed as MLN8237 free acid. The key formulation excipients that aid in the in vivo absorption of the drug are sodium bicarbonate, sodium lauryl sulfate, and enteric coating. The other formulation excipients such as povidone, microcrystalline cellulose, croscarmellose sodium, and sodium stearyl fumarate serve as manufacturing aids.

Open-label investigational product will be labeled to fulfill all requirements specified by applicable governing regulations.

8.1.3 **Preparation and storage:** Alisertib is a cytotoxic compound, and should be handled with caution. Sites should follow institutional hazardous substance procedures for handling, disposal and spill clean-up.

Enteric-coated tablets are packaged in 60-cc HDPE bottles with rayon coil, induction seal, desiccant packs and polypropylene child-resistant caps.

The oral solution is filled in 2-oz. amber polyethylene terephthalate bottles, sealed with 24-mm polypropylene child-resistant caps and polyester liners.

Alisertib should be stored at controlled room temperature (20-25°C) with excursions permitted to 15-30 °C, and used before the retest date provided by the manufacturer.

8.1.4 **Administration:** Retain alisertib in the bottle provided until use.

Alisertib should be administered as provided and is not intended to be manipulated in any way. Alisertib is a cytotoxic anticancer drug. As with other potentially toxic compounds, caution should be exercised when handling. It is recommended that gloves and protective garments be worn during preparation when dispensed in the clinic.

Alisertib may be administered regardless of the timing of meals, unless otherwise specified in the protocol. The dose should be swallowed with 250 mL (about 1 cup) of water. Twice daily doses should ideally be taken every 12 hours, and doses are required to be separated by a minimum of 6 hours. Vomited doses will **not** be made up. Patients will take their next dose at the regularly scheduled time.

8.1.5 **Pharmacokinetic information:** Pharmacokinetics properties of alisertib in patients with hematologic malignancies are generally consistent with those observed in patients with non-hematologic malignancies.

- a) Absorption – Clinical development has transitioned to the enteric-coated tablet formulation which is designed to bypass the stomach and delay dissolution until delivery to the upper small intestine, due to reduced solubility of an acidic drug in acidic pH. ECT absorption is fast with an overall median  $T_{max}$  of 2.5 hours post-dose.
- b) Distribution – Alisertib is highly bound to plasma proteins with percentage of unbound alisertib measured at 2.5% in human plasma. Based on the results of in vitro blood-to-plasma partitioning studies in human whole blood, the mean blood-to-plasma ratio was 0.57, indicating preferential distribution into human plasma.
- c) Metabolism – Alisertib is metabolized by both oxidation and glucuronidation pathways, and multiple cytochrome P450 (CYP) isozymes (CYP3A4, 2C8, 2C9, 2C19, and 1A2) and uridine diphosphate-glucuronosyltransferase (UGT) isozymes (UGT1A1, 1A3, and 1A8) are involved. Phase 1 oxidative metabolism was identified to be of quantitative importance, with an estimated contribution of CYP3A4 of approximately 60% to overall apparent oral clearance in humans. Therefore, moderate to strong inhibitors of CYP3A4 and clinically significant inducers may alter systemic exposures of alisertib. Given a partial contribution of UGT1A1 to the metabolism of alisertib based on in vitro studies, genotyping for the reduced expression allele UGT1A1 \*28 has been prospectively performed in the clinical program across phase 1 and phase 2 studies. The results of these analyses indicate that pharmacogenetic variation in UGT1A1 is not a meaningful contributor to the variability in the clinical PK of alisertib.
- d) Excretion – Overall mean steady-state terminal half-life following multiple-dose administration of enteric coated tablets in patients with non-hematologic

malignancies was approximately 21 hours. Preliminary results indicate the mean terminal half-life for the oral solution is 22 hours. Negligible urinary excretion of alisertib was observed in humans. The predominant route of elimination for alisertib was fecal, consistent with hepatic metabolism and biliary excretion of alisertib.

- 8.1.6 Potential Drug Interactions:** Oxidative metabolism is the predominant route of elimination for alisertib. Results of subsequent in vitro drug metabolism studies have shown that the oxidative metabolism of alisertib is mainly mediated via CYP3A4. Study results have shown that co-administration of alisertib with rifampin (a strong inducer of CYP3A), and itraconazole (a strong inhibitor of CYP3A) have a significant effect on the systemic exposure of alisertib. Therefore, it is recommended that the concomitant use of strong CYP3A inhibitors (e.g., ketoconazole, itraconazole, clarithromycin, conivaptan, nefazodone, telithromycin, voriconazole, posaconazole, boceprevir, telaprevir, and grapefruit juice/grapefruit containing products) and strong CYP3A inducers (e.g., rifampin, enzyme-inducing antiepileptic agents), be avoided in patients receiving alisertib. Selection of an alternate concomitant medication with no or minimal CYP3A inhibition potential is recommended. If co-administration of strong CYP3A inhibitors is medically necessary, investigators should monitor for toxicities and follow the dose modifications for toxicity per study protocol.

Alisertib exhibits pH-dependent solubility with decreased solubility under acidic pH conditions. Results from a completed study evaluating the effect of esomeprazole on alisertib PK indicated that co-administration of alisertib with esomeprazole resulted in a 28% increase in total systemic exposure of alisertib. Co-administration with drugs that alter intragastric pH (e.g. PPIs, H2 antagonists) is not permitted in ongoing clinical studies. Studies also prohibit concomitant use of pancreatic enzymes or conditions (such as pancreatectomy) that could potentially impact drug absorption in the upper bowel.

- 8.1.7 Known potential toxicities:**
- Very common (>10%): anemia, febrile neutropenia, leukopenia, neutropenia, thrombocytopenia, abdominal pain, diarrhea, nausea, oral pain, stomatitis, vomiting, asthenia, fatigue, pyrexia, decreased appetite, dehydration, somnolence, disorientation (and associated memory loss), alopecia
- Common ( $\geq 1\%$  and  $< 10\%$ ): lymphopenia, pancytopenia, dyspepsia, mucosal inflammation, URTI, UTI, pneumonia, oral candidiasis, sepsis (including fatal sepsis), cellulitis, oral herpes, sinusitis, nasopharyngitis, bronchitis, herpes zoster, influenza, conjunctivitis, esophagitis, skin infection, fungal skin infection, oral fungal infection, septic shock, increased AST, increased ALT, increased blood bilirubin, increased alkaline phosphatase, increased GGT, gait disturbance, confusional state, rash, pruritic rash, macular rash, maculo-papular rash, dermatitis acneiform, palmar-plantar erythrodysesthesia syndrome
- Uncommon ( $\geq 0.1\%$  and  $< 1\%$ ): sedation, dermatitis bullous

Reproductive toxicology studies have not been conducted with alisertib. Given the outcomes associated with Aurora A kinase inhibition and the effects of alisertib observed in reproductive tissues in repeat-dose toxicology studies, it is anticipated that alisertib could be a reproductive and developmental toxicant.

Because alisertib may cause anemia, neutropenia, leukopenia, lymphopenia, and thrombocytopenia, patients on alisertib may experience the anticipated sequelae of infection, hemorrhage, or bleeding.

Because of the effects of alisertib on the gastrointestinal mucosa, there is a potential risk of mucosal bleeding, GI bleeding, and the associated infections and sepsis.

Cases of cardiac abnormalities have been infrequently observed in patients receiving treatment with alisertib, including decreased left ventricular ejection fraction, tachycardia, and 1 case of QT prolongation. The causal relationship between cardiac dysfunction and alisertib has been confounded by patients' prior history of other cardiac abnormalities.

Alisertib is structurally related to the benzodiazepines and may cause somnolence, confusion, dizziness or gait disturbance associated with the onset of maximal plasma concentration (about 3 hrs post-dose). For this reason, patients should not drive, operate dangerous machinery, or perform any other task requiring full alertness and/or coordination if these effects are experienced while enrolled on study. Sedative effects have been managed by administration of divided doses and dose administration at bedtime, although dose reductions have sometimes been required.

